SUMMARY OF CHANGES

For Protocol Amendment 9, Version 2.0

NCI Protocol #: CITN-09
Local Protocol #: CITN-09

Protocol Date: May 22, 2018

I. Changes Requested by CTEP

#	Section	Pages	Revision
1.	7.1.1	71-76	
Updated CAEPR content to version 2.4 per CTEP Request for Rapid Amendment dated 4/26/18. Updated risks following CAEPR table. The following changes are incorporated:
 
 • Added New Risk: 
 • Less Likely: Immune system disorders - Other (sarcoidosis) • Rare but Serious: Immune system disorders - Other (acute graft-versus-host-disease); Metabolism and nutrition disorders - Other (diabetic ketoacidosis); Metabolism and nutrition disorders - Other (type 1 diabetes mellitus); Nervous system disorders - Other (non-infectious encephalitis); Nervous system disorders - Other (non-infectious meningitis); Palmar-plantar erythrodysesthesia syndrome • Increase in Risk Attribution: 
 • Changed to Less Likely from Also Reported on MK-3475 Trials But With Insufficient Evidence for Attribution: Abdominal pain; Back pain; Cough; Hyponatremia • Provided Further Clarification: 
 • Footnotes have been reordered. • Footnote #2 has been updated and now reads: “Immune-mediated adverse reactions have been reported in patients receiving MK-3475 (pembrolizumab). Adverse events potentially related to MK-3475 (pembrolizumab) may be manifestations of immune-mediated adverse events. In clinical trials, most immune-mediated adverse reactions were reversible and managed with interruptions of MK-3475 (pembrolizumab), administration of corticosteroids and supportive care.” • Footnote #3 has been added and reads: “Acute graft-versus-host disease has been observed in patients treated with MK-3475 (pembrolizumab) who received hematopoietic stem cell transplants.” • Thrombotic thrombocytopenic purpura, previously listed under the IMMUNE SYSTEM DISORDERS SOC (CTCAE 4.0 language), is now listed under the BLOOD AND LYMPHATIC SYSTEM DISORDERS SOC.

#	Section	Pages	Revision

To submit site registration documents:	For patient enrollments:	To submit study data

Regulatory documentation must be submitted to the CTSU via the Regulatory Submission Portal:
 
Regulatory Submission Portal (Sign in at www.ctsu.org, and select the Regulatory Submission sub-tab under the Regulatory tab.)
 
Institutions with patients waiting that are unable to use the Portal should alert the CTSU Regulatory Office immediately at [name] to receive further instruction and support.
 
Contact the CTSU Regulatory Help Desk at [name] for regulatory assistance.
	
Please refer to the patient enrollment section for instructions on using the Oncology Patient Enrollment Network (OPEN) at https://www.ctsu.org/OPEN_SYSTEM/ or https://OPEN.ctsu.org.
 
Contact the CTSU Help Desk with any OPEN-related questions at [contact].
	
Data collection for this study will be done via Medidata Rave (FHCRC/AXIO Research, Inc.). Please refer to the data submission section of the protocol for Medidata Rave instructions.

The most current version of the study protocol and all supporting documents must be downloaded from the protocol-specific Web page of the CTSU Member website located at https://www.ctsu.org. Access to the CTSU members' Web site is managed through the Cancer Therapy and Evaluation Program - Identity and Access Management (CTEP-IAM) registration system and requires user log on with CTEP-IAM username and password. Permission to view and download this protocol and its supporting documents is restricted and is based on person and site roster assignment housed in the CTSU RSS.
		

For clinical questions (i.e. patient eligibility or treatment-related): Contact the CITN Central Operations and Statistical Center at [contact] or [contact]
		

For nonclinical questions (i.e. unrelated to patient eligibility, treatment, or clinical data submission) contact the CTSU Help Desk by phone or email: CTSU General Information Line – [name], or [contact]. All calls and correspondence will be triaged to the appropriate CTSU representative.
		

The CTSU Web site is located at https://www.ctsu.org.
		

STUDY SUMMARY

Abbreviated Title	Merkel Cell Carcinoma (MCC) Therapy with MK-3475
Trial Phase	Phase II
Clinical Indication	Advanced stage MCC: Locally advanced or metastatic
Trial Type	Single Arm, Simon Two-Stage, Therapeutic
Type of control	Nonrandomized trial with primary end point of overall response rate (ORR). Secondary endpoint of progression-free survival (PFS) will be compared to recent historical controls receiving standard chemotherapy.
Route of administration	Intravenous (IV)
Trial Blinding	None
Treatment Group	MK-3475, 2 mg/kg every 3 weeks (q3wks)
Number of trial patients	Initial enrollment included 26 patients. Twenty-four (24) additional patients -were enrolled to provide an expanded safety and efficacy profile.
Estimated duration of trial	The first 26 patients were enrolled over 11 months. The additional 24 patients were enrolled over the following 18 months. Study to continue for up to 2 years beyond enrollment plus follow-up of last subject.
Duration of Participation	Each patient will participate in the trial from the time the Informed Consent Form (ICF) is signed through final protocol-specified contact. After a screening phase for eligibility, patients will receive MK-3475 every 3 weeks. Treatment for patients that achieve a stable disease (SD) or a partial response (PR) can continue for a maximum of 2 years. If progression is confirmed at week 17 or beyond, patients will be eligible to continue treatment with MK-3475 if otherwise clinically stable. Patients that achieve a complete response (CR) can discontinue treatment after 6 months of therapy provided the patient has had at least 2 cycles past validation of CR. At the discretion of the investigator, these patients will be eligible for retreatment if they experience disease progression, as long as they meet the criteria for retreatment and the trial is ongoing. Patients who have received 2 years of treatment on study and have a PR or SD and then progress, may be eligible for retreatment. Administration of MK-3475 will be stopped with: documented disease progression warranting alternative systemic therapy, $\geq 25\%$ increase in tumor burden following initial confirmation of PD, unacceptable adverse event(s), intercurrent illness that prevents further administration of

	
treatment, investigator's decision to withdraw the patient, patient withdraws consent, pregnancy of the patient, noncompliance with trial treatment or procedure requirements, or administrative reasons.
 
After the end of treatment, each patient will be followed for 30 days for adverse event monitoring (serious adverse events will be collected for 90 days after the end of treatment with investigator attribution as to whether the SAE is associated with MK-3475 or subsequent therapies). After the Post-Treatment Safety Follow-Up Visit, patients will be followed for survival via phone contact every 12 weeks.
 
Patients who discontinue study therapy without documented disease progression should continue to be monitored for disease status by radiologic imaging according to the guidelines described in the Study Schema for post-treatment follow-up.

--	--

Overall Trial Schema (PD1 Trial Timeline_v10Jun16)

Patient Visit Timeline (dosing, scans and biomarkers)

[figure not shown]
[figure not shown]

TABLE OF CONTENTS

1.	OBJECTIVES	10
1.1	Primary Objectives.....	10
1.2	Secondary Objectives.....	10
1.3	Exploratory Objectives	10
2.	BACKGROUND	11
2.1	Study Disease.....	11
2.2	CTEP IND Agent: MK-3475	19
2.3	Other Agent(s): N/A	23
2.4	Rationale for Trial of MK-3475 in Merkel Cell Carcinoma Patients	23
2.5	Correlative Studies Background	26
3.	PATIENT SELECTION	31
3.1	Eligibility Criteria	31
3.2	Exclusion Criteria	33
3.3	Inclusion of Women and Minorities	36
4.	REGISTRATION PROCEDURES	36
4.1	Investigator (IVR), Non-Physician Investigator (NPIVR), and Associate Plus (AP) Registration with CTEP	36
4.2	Site Registration.....	38
4.3	Patient Registration.....	39
4.4	General Guidelines.....	40
5.	TREATMENT PLAN.....	41
5.1	Agent Administration.....	42
5.2	Definition of Dose-Limiting Toxicity: N/A.....	50
5.3	General Concomitant Medication and Supportive Care Guidelines	50
5.4	Duration of Therapy.....	51
5.5	Duration of Follow Up.....	52
5.6	Criteria for Removal from Study	53
5.7	Criteria to Resume Treatment.....	53
5.8	Treatment Beyond Progression.....	54
5.9	Discontinuation of Treatment Following Complete Response.....	55
5.10	Retreatment with MK-3475 of patients with recurrence	55
5.11	Beginning and End of the Trial.....	56
6.	DOSING DELAYS/DOSE MODIFICATIONS	56
6.1	MK-3475 Dose Modifications	56
6.2	Delayed Visits for Reasons Other Than Toxicity.....	70
7.	ADVERSE EVENTS: LIST AND REPORTING REQUIREMENTS	70

1. OBJECTIVES

The goal of this trial is to determine the antitumor efficacy of MK-3475 in patients with advanced Merkel cell carcinoma (MCC). The trial is an open-labeled, non-randomized trial with a Simon two-stage design. Patients who have not received any previous systemic therapy for their disease will be treated with MK-3475 2 mg/kg administered every 3 weeks. Objective responses and disease progression will be monitored by computed tomography (CT) scans and assessed by Response Evaluation Criteria in Solid Tumors, version 1.1 (RECIST 1.1).

1.1 Primary Objectives

To determine the clinical efficacy of MK-3475 as the first systemic intervention for patients with advanced MCC.

The primary endpoint will be objective response rate (ORR) as measured by RECIST 1.1.

Hypothesis: Cellular immunity plays a major role in the outcome of MCC. Thus, therapy with MK-3475 will induce substantial objective responses and a portion of the responses will be durable.

1.2 Secondary Objectives

To determine the clinical activity of MK-3475 as the first systemic intervention for patients with advanced MCC.

The secondary endpoints will be progression-free survival (PFS), duration of response (DOR) and overall survival (OS), as measured by RECIST 1.1. The PFS will be determined at 16 months and compared to the historical PFS for patients treated with chemotherapy, which is 5% at 16 months.

- Progression-free survival (PFS)
- Duration of response (DOR)
- Overall survival (OS)

Hypothesis: Because of the strong links between cellular immunity and MCC survival, responses to MK-3475 are likely to be more durable, as assessed at 16 months, than responses to the selected comparator, recent historical controls treated with systemic chemotherapy, which tends to be immunosuppressive.

1.3 Exploratory Objectives

To determine the immune correlates of the clinical activity of MK-3475

The endpoints will include immunohistochemical (IHC) and gene expression analysis, whole exome sequencing, and neoantigen identification focusing on delineating the immune components and immunologic milieu within the tumor before therapy. The IHC analytes will include, but are not limited to Merkel cell polyomavirus (MCPyV) tumor antigen (T-Ag), programmed cell death 1 (PD-1), and its ligand 1 (PD-L1), CD8, CD3, CD68, CD45, and CD56. In addition, MCPyV viral DNA will be quantified in the tumor and T cell receptor sequencing in tumor infiltrating lymphocytes (TIL) will be performed where pre- and post-treatment biopsies

are available. Cellular and humoral MCPyV-specific immune responses will be assessed with Enzyme-Linked ImmunoSpot (ELISpot) serology assays in blood samples at baseline, after initiating MK-3475 therapy, and correlated with clinical responses over time. Among patients with corresponding major histocompatibility complex (MHC)-peptide tetramers, pre-and post-treatment samples of circulating MCPyV-specific CD8 T cells will be isolated by flow cytometry and subjected to deep immunophenotyping by messenger RNA (mRNA) expression analysis.

Hypothesis: MK-3475 will enhance functional activity of MCC-specific lymphocytes and facilitate tumor regression. Thus, the clinical endpoints associated with tumor regression and durability of response will be correlated with the pretreatment levels and type of immune cell infiltration in the tumor, PD-1 and PD-L1 expression and association in the tumor, or systemic measures of immune response to tumor-specific viral MCPyV antigens.

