2. BACKGROUND

2.1 Study Disease

MCC is an aggressive skin cancer with a 5-year disease-associated mortality of 46% [[Lemos 2010](#)]. Nearly 50% of patients with MCC develop distant disease typically within 2 to 3 years of diagnosis. Systemic chemotherapy is commonly used, but is fairly toxic with limited, transient efficacy. The reported incidence of MCC has quadrupled in the past 20 years to an estimated ~1600 cases/year in the United States [[Hodgson 2005](#); [Albores-Saavedra 2010](#)]. This increasing incidence is partly due to improved detection using a specific IHC marker, cytokeratin-20, [[Moll 1992](#)] but may also be due to the higher prevalence of known risk factors for MCC: chronic T-cell immune suppression [[Penn 1999](#); [Engels 2002](#); [Heath 2008](#)] and the number of Caucasians over 50 years of age with extensive prior sun exposure [[Heath 2008](#)]. Despite its growing health impact and aggressive behavior, very few clinical trials have focused on this disease. There is an unmet need for biology-driven therapy in MCC.

MCC is causally associated with the MCPyV [[Feng 2008](#), [Houben 2010](#), [Rodig 2012](#)]. The viral T-Ag oncoproteins, present in approximately 80% of MCC tumors, are required for ongoing tumor growth [[Houben 2010](#)]. The cellular immune response is strongly linked to outcome in MCC. Specifically, intratumoral CD8+ lymphocyte infiltration is associated with improved survival independent of stage at presentation [[Paulson 2011](#)]. MCPyV-specific T cells have been isolated from the blood and tumors of patients with MCC and track with disease burden.

PD-1 is likely playing a key role in MCC immune evasion in many patients [[Afanasiev 2013](#)]. The PD-1 receptor-ligand interaction is a major pathway hijacked by tumors to suppress immune control. The normal function of PD-1, expressed on the cell surface of activated T cells is to downmodulate unwanted or excessive immune responses, including autoimmune reactions. Over 90% of MCPyV-specific T cells express PD-1. The fact that PD-1 expression is high on these T cells, in combination with frequent expression of related T-cell immunoglobulin mucin-3 (TIM-3), suggests T-cell exhaustion/dysfunction is prevalent. Although these virus-specific T cells are present in many patients with MCC, they often fail to control progression of MCC, potentially due to immune evasion and exhaustion.

2.1.1 *Merkel cell polyomavirus (MCPyV) and MCC*

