The persistent expression of MCPyV oncoproteins in MCC provides a unique opportunity to characterize immune evasion mechanisms in this cancer. Patients with MCPyV-positive MCC tumors frequently have T cells specific for these persistently expressed oncoproteins [[Iyer 2011](#)]. We hypothesized that these MCPyV-specific T cells, although present in the blood of patients with MCC, were unable to eliminate MCC tumors, either because they were dysfunctional and/or due to the other immune evasion mechanisms. We determined the presence and functional status of tumor-infiltrating lymphocytes (TIL, n=7) and virus-specific peripheral blood T cells from 18 patients with MCC and 10 control patients. MCPyV-specific CD8 T cells were detected directly ex vivo from the blood of 7 of 11 (64%) patients with MCPyV-positive tumors. In contrast, 0 of 10 control patients had detectable levels of these cells in their blood ($P<0.01$) [[Afanasiev 2013](#)]. MCPyV-specific T cells in serial blood specimens increased with MCC disease progression and decreased with effective disease therapy. Because T-cell number increases with disease burden, there is a need for careful interpretation of immunotherapy efficacy data aimed at increasing tumor-specific T-cell frequency. The presence and expansion of MCC-specific T cells with increasing tumor burden is highly suggestive that tumor immune escape mechanisms are active in MCC.

2.1.4 ***Active Immune Evasion Mechanism in MCC***

In MCC tumors, PD-L1 expression within the tumor microenvironment has been observed and is positively correlated with the number of infiltrating CD8 lymphocytes using both histologic and mRNA-based analyses in independent cohorts [[Afanasiev 2013](#); [Lipson 2013](#)]. Over 90% of MCPyV-specific T cells express PD-1 (as compared with approximately 30% of all CD8+ T cells, approximately 50% of cytomegalovirus [CMV]-specific T cells, and approximately 80% of Epstein-Barr virus [EBV]-specific T cells).

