Key questions that these correlative studies will address include: (1) Will the surface marker phenotype and/or transcriptional state of a patient's "exhausted" tumor-specific PD-1+ CD8 T cell predict response to MK-3475?; (2) Does the surface marker phenotype and/or transcriptional state of a patient's "exhausted" tumor-specific PD-1+ CD8 T cells correlate with features such as CD8 infiltration in the pretreatment tumor? And, are these features modulated with MK-3475 treatment?; and (3) Will PD-1+ T cells from nonresponding patients be characterized by a specific pattern of gene regulation, mutanome landscape or neoantigen array compared to those of responders? Specifically, are additional counter-regulatory immune modulators expressed to compensate for PD-1 blockade? If so, these secondary counter-regulatory immune modulators may represent relevant targets to overcome resistance to PD-1 therapy.

ELISpot analysis will be performed by the CITN Immune Monitoring Laboratory under the direction of [name]. ICS analyses will be performed by the laboratory of [name] at FHCRC.

2.5.4 ***Merkel Cell Polyomavirus–Specific Antibody Responses—Laboratory Correlative Studies #6***

Because antibody titers for the T-Ag oncoprotein are a marker of disease burden and immune responsiveness to the virus, we will also test for these antibodies at baseline [[Paulson 2010](#)]. If positive, this assay will be carried out on serum collected at the time of scans. We anticipate that 50% of patients will make antibody to the MCPyV oncoprotein. Key questions include (1) Are seropositive patients more likely to respond to anti-PD-1? and (2) Do antibody titers provide greater or different insights into responses than gold-standard imaging studies? In several cases, rises in oncoprotein antibody have occurred before detection of disease by CT and may herald early immune recognition of recurrent disease. This serologic assay will be performed by Luminex and carried out by the CLIA-certified Clinical Immunology Laboratory, Department of Laboratory Medicine, at the UW in conjunction with [name] lab.

2.5.5 ***Quantification of PBMC and T-cell Subsets—Laboratory Correlative Study #7***

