3. PATIENT SELECTION

3.1 Eligibility Criteria

In order to be eligible for participation in this trial, the patient must:

- 3.1.1 Patients must have biopsy-proven metastatic MCC or locoregional MCC that has recurred following standard locoregional therapy with surgery and/or radiation therapy.
- 3.1.2 Patients must have measurable disease per RECIST 1.1 assessed by CT scan, or for skin lesions not measurable by CT scan, measurements may be performed with caliper or flexible ruler.

Note: Stage IV no evidence of disease (NED) is excluded by this criterion.
- 3.1.3 Be ≥ 18 years of age on day of signing informed consent

Note: Because no dosing or AE data are currently available on the use of MK-3475 in patients < 18 years of age, children are excluded from this study.
- 3.1.4 Have a performance status of ≤ 1 on the Eastern Cooperative Oncology Group (ECOG) Performance Scale (see Appendix A)
- 3.1.5 Life expectancy of greater than 6 months
- 3.1.6 Patients must have normal organ and marrow function (all screening labs should be performed within 14 days of treatment initiation) as defined below:

System	Laboratory value
- leukocytes	$\geq 2,000/\text{mcL}$
- absolute neutrophil count	$\geq 1,500/\text{mcL}$
- platelets	$\geq 100,000/\text{mcL}$
- hemoglobin	$\geq 9 \text{ g/dL}$ OR $\geq 5.6 \text{ mmol/L}$

- serum total bilirubin ≤ 1.5 X upper limit of normal (ULN) OR direct bilirubin \leq ULN for patients with total bilirubin levels >1.5 X ULN
- AST(SGOT)/ALT(SGPT) ≤ 2.5 \times institutional ULN OR ≤ 5 X ULN for patients with liver metastases
- serum creatinine ≤ 2.5 X ULN
- Measured or calculated^a creatinine clearance (CrCl) (Glomerular filtration rate [GFR] can also be used in place of creatinine or CrCl) ≥ 30 mL/min for subject with creatinine levels >2.5 X institutional ULN

OR

- Thyroid Stimulating Hormone (TSH) Within Institutional Limits (ie: Normal). If TSH is greater or less than institutional limits patients may participate if their T4 is WNL. Patients may be on a stable dose of replacement thyroid medication. Dose adjustments are allowed if needed.

^aCreatinine clearance should be calculated per institutional standard.

3.1.7 Patients must provide tissue from an archival tumor sample or newly obtained core, punch or excisional biopsy of a tumor lesion if deemed relatively safe and technically feasible.

Note: Newly obtained biopsy is preferable.

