PFS and OS by the following biomarker categories: 
 • pre-therapy CD8+ • pre-therapy CD3+ T-cell infiltration in tumor • pre-therapy PD-1 and PD-L1 expression in tumor, 
 • * pre-therapy immune response to MCPyV 	Descriptive statistics	Eligible subjects who receive at least 1 dose of treatment	censored at last assessment

ORR by the following biomarker categories:
 
 • pre-therapy CD8+ • pre-therapy CD3+ T-cell infiltration in tumor • pre-therapy PD-1 and PD-L1 expression in tumor, 
* pre-therapy immune response to MCPyV
	
Descriptive statistics
	
Eligible subjects who receive at least 1 dose of treatment
	
Missing value considered nonresponder

--	-------------------------------	---	--

Note: PD after 1 or more missed visits will be counted as PD as of the date of documented disease progression. An additional sensitivity analysis will be performed where subjects with 2 or more missed visits before progression will be censored at the last disease assessment before the ≥ 2 missed disease assessments.

13.5.2 *Statistical Methods for Safety Analyses*

Safety and tolerability will be assessed by clinical review of all relevant parameters including adverse experiences, laboratory tests, vital signs, and ECG measurements.

Adverse experiences will be summarized as counts and frequencies by toxicity grade. Summary statistics (median and range) for time to onset of first drug-related toxicity will be provided.

Laboratory assessments, vital signs, and other safety endpoints will be summarized using descriptive statistics as appropriate.

13.5.3 *Summaries of Baseline Characteristics, Demographics, and Other Analyses*

The number and percentage of subjects enrolled, and the primary reason for discontinuation will be displayed. Demographic variables (such as age) and baseline characteristics will be summarized either by descriptive statistics or categorical tables. No statistical hypothesis tests will be performed on these characteristics.

13.6 **Multiplicity**

The treatment comparison will be tested at one sided 5% alpha level and no multiplicity adjustment will be applied.

13.7 **Sample Size/Accrual Rate and Power Calculations**

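### Table 13.1 describes outcome by anti-MCPyV immune response in all treated patients without also showing it by tumor viral status, so the pooled contrast cannot separate absent viral antigen from absent response to it

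*Combined protocol and SAP*

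**What the plan says.** - **Hypothesis.** Section 1.3 expects tumor regression and durability of response to correlate with several markers, one of which is "systemic measures of immune response to tumor-specific viral MCPyV antigens".
- **Analysis.** Among the exploratory rows of Table 13.1 (section 13.5.1.2), PFS and OS, and separately ORR, are described by "pre-therapy immune response to MCPyV". The population is "Eligible subjects who receive at least 1 dose of treatment" and the method is "Descriptive statistics". The opening of section 13 says there will be no separate SAP, so this table is the analysis plan.
- **Who is enrolled.** Section 3.1.1 states: "Patients must have biopsy-proven metastatic MCC or locoregional MCC that has recurred following standard locoregional therapy with surgery" (and/or radiation). No criterion concerns the virus.
- **How often the virus is present.** Section 2.1 states: "The viral T-Ag oncoproteins, present in approximately 80% of MCC tumors, are required for ongoing tumor growth". Section 2.1.1 gives about 80% to 95%.
- **Link between virus and marker.** Section 2.1.3 states: "Patients with MCPyV-positive MCC tumors frequently have T cells specific for these persistently expressed oncoproteins". Its detection rate, 7 of 11, is for patients with virus-positive tumors.
- **What is measured.** Section 2.5.2 determines tumor viral status by IHC and by PCR. Section 2.5.3.3 (study #5) tests T-cell responses in every patient, and section 2.5.4 (study #6) tests baseline antibody.
- **Where viral status enters an outcome analysis.** It is a separate predictor of response (section 2.5, question 1; section 2.5.2), and section 2.5.3.3 relates it to epitope spreading. It is not a row, stratum or restriction in Table 13.1.

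**The concern.** The hypothesis is about viral antigens that belong to the patient's tumor. In a virus-negative tumor MCPyV antigens are not tumor antigens, so a low or absent anti-MCPyV response there has a different meaning. In a virus-positive patient it means that no immunity to an available tumor antigen was detected. In a virus-negative patient it means that there was no such antigen. An analysis by category of immune response in all treated patients puts both kinds of patient together unless the plan separates them.

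The protocol itself treats viral status as a possible predictor of outcome. Section 2.5 asks whether virus-positive tumors respond more often (question 1), and whether neoantigen differences between virus-positive and virus-negative tumors go with response (question 10). Viral status is therefore plausibly related to both the marker and the outcome, which makes it a candidate confounder of this contrast. What is at stake is the interpretation of one exploratory correlate: a difference could be read as an effect of antiviral immunity when part of it reflects viral status, or a real effect could be hidden.

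**Working it through.** The plan states no figure for this analysis, so there is none to reproduce. The check asks how large the virus-negative share of the low or absent response group could be, and how far that share could move the contrast.

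**Inputs**
- N = 50 (section 13.7).
- Virus-positive share v = 0.80 (section 2.1) to 0.95 (section 2.1.1).
- Antibody-positive share of all patients: 50% (section 2.5.4).
- T cells detectable in virus-positive patients: 7/11 = 64% (section 2.1.3).
- Assumption: virus-negative patients show no anti-MCPyV response. The documents give no rate for them. The 0 of 10 in section 2.1.3 concerns controls, and T cells only.

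**Step 1: virus-negative share of the low or absent response group**

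w = N(1 − v) / (N − number with a response). The number with a response is 0.50N for antibody and (7/11)vN for T cells.

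| Marker | v | Virus-negative | With response | Low or absent | w |
|---|---|---|---|---|---|
| Antibody | 0.80 | 10 | 25 | 25 | 10/25 = 40% |
| T cells | 0.80 | 10 | 25.5 | 24.5 | 10/24.5 = 41% |
| Antibody | 0.95 | 2.5 | 25 | 25 | 2.5/25 = 10% |
| T cells | 0.95 | 2.5 | 30.2 | 19.8 | 2.5/19.8 = 13% |

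**Step 2: effect on the contrast (all ORRs assumed)**

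Take the antibody split, with ORR of 60% with a response and 40% without one among virus-positive patients. The true difference is 20 points. With ORR c in virus-negative patients, the pooled difference is 0.60 − [w·c + (1 − w)·0.40].

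| c | w = 0.40 | w = 0.10 |
|---|---|---|
| 20% | 0.60 − 0.32 = 28 points | 22 points |
| 40% | 0.60 − 0.40 = 20 points | 20 points |
| 60% | 0.60 − 0.48 = 12 points | 18 points |

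If antiviral immunity had no effect among virus-positive patients, but ORR differed by 20 points between virus-positive and virus-negative tumors, the pooled contrast would show a spurious difference of w × 20. That is 8 points at w = 0.40 and 2 to 3 points at w = 0.10 to 0.13.

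**Step 3: precision**

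Approximate 95% half-width for 60% versus 40%:
- All comers, 25 versus 25: 1.96 × √(0.24/25 + 0.24/25) = 27 points.
- Virus-positive only at v = 0.80, 25 versus 15: 1.96 × √(0.24/25 + 0.24/15) = 31 points.

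**The case against.** Several points on the other side are sound.

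- **The plan defines no category of non-response.** Table 13.1 refers to biomarker categories and sets no cut-point. A reader might infer that the plan places virus-negative patients in a negative group. It does not say so. The mixing follows only if the rows are produced as written and virus-negative patients test low or negative. If some test positive, they enter the other group, where the measured response is again not to an antigen of their tumor.
- **The seropositivity questions are all-comer questions.** Section 2.5.4 asks: "Are seropositive patients more likely to respond to anti-PD-1". Question 4 of section 2.5 is equally unrestricted. A reader might infer that the trial cannot answer its own correlative question. The pooled contrast does answer these two. What it does not isolate is the tumor-antigen hypothesis of section 1.3. For the same reason, replacing the population by virus-positive patients only would be a debatable change of estimand.
- **Viral status is not ignored.** Response by viral status is planned as its own question. Two separate one-way summaries, however, do not show the immune-response contrast within virus-positive tumors.
- **The size is uncertain.** The 40% share needs the lowest prevalence. The 7 of 11 has an exact 95% interval of roughly 31% to 89%, and comes from direct ex vivo detection in an earlier study, whereas this trial tests all patients by ELISpot or ICS. Every ORR in the illustration is assumed, and shifts of 8 points lie well inside sampling error.
- **No decision rests on these rows.** They carry no test and no alpha.

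These points limit the severity and argue against replacing the population. They do not argue against an added breakdown.

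**Conclusion.** The point holds as a minor one. As written, the Table 13.1 rows for immune response to MCPyV cannot separate a missing viral antigen from a missing response to it, although section 1.3 is about tumor-specific viral antigens and the data needed to separate them are collected. If virus-negative patients show no anti-MCPyV response, they form about 40% of the low or absent response group at 80% virus-positive and 10% to 13% at 95%. Under the assumed ORRs, a true 20-point difference would appear as 12 to 28 points in the first case and 18 to 22 in the second (antibody split). The direction of the distortion is unknown, because it depends on how virus-negative tumors respond. The primary ORR analysis and the secondary PFS, DOR and OS analyses are unaffected.

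**What to change.** - Keep the all-comer rows of Table 13.1 for ORR, PFS and OS by immune response to MCPyV.
- Add to the same rows a breakdown by tumor viral status from section 2.5.2: immune response present versus absent within virus-positive tumors, virus-negative patients as their own group, and patients with unknown or discordant IHC and PCR results listed separately.
- State that the section 1.3 hypothesis will be interpreted from the contrast within virus-positive tumors.
- Apply the same breakdown where studies #5 and #6 are correlated with outcome. Studies #3 and #4 need it less, because they depend on tetramer-matched patients with detectable virus-specific T cells (about 25% by section 2.5.3.2).

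This needs no new samples or assays. The opening of section 13 already lets changes to exploratory analyses be documented, with timing and reason, in the clinical study report. The price is precision: about 40 instead of 50 patients in the within-virus-positive contrast at 80% positive (47.5 on average at 95%), with the half-width in the example growing from about 27 to 31 points at 80%.
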